8.4 Evaluation of Safety

The primary safety objective of this study is to evaluate the feasibility and safety of vaccination with type-1-polarized dendritic cells (α DC1) loaded with apoptotic allogeneic tumor and tumor-unrelated “heterologous helper antigens”. Based on the past experience from the University of Pittsburgh Cancer Institute (UPCI) and other clinical centers performing DC-based vaccinations, our hypothesis is that the vaccination with DC will be well-tolerated, and not associated with serious adverse side effects.

8.5 Measurement of the Immunologic Effects

The immunologic endpoints of this study will include an in vivo assessment of DTH responses against the allogeneic tumor cell lysate, and (on additional sites) responses to the “heterologous helper antigen” KLH. In addition, we will perform the in vitro assessment of the increase in the frequency of circulating tumor-specific T-cells as determined by IFN γ ELISPOT against the allogeneic tumor cells used in the vaccine and in case of HLA-A2+ subjects against the individual TAAs relevant to prostate cancer (Table 1). All of the subjects will be tested for PMBC responses to KLH. To allow for these evaluations, 70 cc of peripheral blood will be drawn 4 times (1 x pre- and 3 times post-vaccination, see study calendar). As additional tertiary endpoints, we will perform and IFN γ and IL-5 ELISPOT, and cytotoxicity assays. EPIMAX analysis will be used to define the magnitude and cytokine production profiles of CD4⁺ and CD8⁺ T cell responses to the overlapping peptide libraries and individual peptides covering the entire span of PAP and PSMA molecules.

8.5.1 Immunologic Assays

- DTH against the allogeneic tumor cell lysate and (on additional sites) to the “heterologous helper antigen” KLH. Following the readout, the subjects will be asked for a separate consent for a biopsy of the DTH test site to perform the in situ and ex vivo analyses of the DTH-infiltrating T cells.
- Cytokine production in ELISPOT assay (IFN γ /IL-5), using the cells isolated from 70 cc of peripheral blood will be used to detect the frequencies of IFN γ -producing CTLs.

- In all HLA-A2 subjects we will also test the responses to all individual TAAs identified in Table 1.
- All of the subjects will be tested for the responses against the whole tumor cells, against KLH and against recombinant PAP and PSA proteins, in order to evaluate the overall increase and the anticipated vaccination-induced Th2 to Th1 shift of CD4⁺ Th cell responses.
- EPIMAX analysis will be used to define the magnitude and cytokine production profiles of CD4⁺ and CD8⁺ T cell responses to PAP and PSMA molecules. The reactivity will be first tested against the pooled batches of the overlapping peptide libraries. Any “positive” pools will be subdivided into individual peptides, in order to define fine specificity of the responses. This analysis will allow us to cover all length of PSMA and PAP, in any subject, independently on HLA type, allowing us to detect immune responses to the previously-identified and potentially novel epitopes.
- We will also analyze CTL cytotoxic activity [to additionally confirm the results of ELISPOT assays],
- We will also monitor the overall numbers of CD4⁺ and CD8⁺ T cells, as well as the frequencies of undesirable CD4⁺/CD25⁺/FoxP3/GITR⁺/ Treg cells. In case of success, these additional novel parameters may be then included in the overall evaluation of this clinical study as additional tertiary end-points.

8.5.2 DTH Testing

Delayed-type hypersensitivity is an in vivo assessment of inflammatory Th1-type T-lymphocyte reactivity against specific antigens. It is the only in vivo assay currently available for the measurement of cellular immunity in humans. A positive DTH response against antigen at cutaneous injection sites will be defined as an increase of 3 mm of induration post dendritic cell vaccine over pre-dendritic cell vaccine. Vehicle only will be used as a negative control in both pre- and post- dendritic cell vaccine evaluations. At each time-point, individual separate sites will be injected with the allogeneic tumor cells used in the vaccine (100 µL in lysate form) and with KLH (100 µg KLH in 200 µL 0.9% sodium chloride). Intradermal injection of saline alone will be used as the negative controls (100 µL 0.9% sodium chloride). Place 3 intradermal injections containing the following (from IMCPL lab):

- 1) 100 µL of allogeneic tumor cells vaccine (cell line)
- 2) 100 µg KLH in 200 µL 0.9% sodium chloride
- 3) 100 µL 0.9% sodium chloride for Negative Control

All testing will be performed on the anterior forearm separated by at least 2 cm in the vertical and horizontal axis. Tattooing of the DTH sites will be done using permanent marker to assure that the site is not injected twice. Skin tests will be read at 48-72 hours by trained clinical personnel.

DRUG FORMULATION AND PROCUREMENT

8.6 Alpha-1 Polarized Dendritic Cells Loaded with Allogeneic Apoptotic Cells

Manufacture of the vaccine will take place in the IMPCL, accordingly to the cGMP-compliant procedures.

8.7 LNCaP Cell Line

The GMP grade cell line (*See Appendix IV and the letter from our collaborator, [name]*) received from Baylor Institute is maintained by the UPCI IMCPL.

8.8 LHRH Analogue

We will plan on using the q 3 month depot preparation of either Goserelin Acetate 10.8 mg (Zoladex) (NSC-606864) or ELIGARD[®] 22.5 mg (Lupron) for once every 3 month dosing (NDA #21-379).

8.8.1 Goserelin Acetate

Chemical Structure: pyro-Glu-His-Trp-Ser-Tyr-D-Ser (But)-Leu-Arg-Pro-Azgly-NH₂

Molecular Weight: 1269 daltons (as base)

Solubility: Soluble in water, dimethylformamide, dimethylsulfoxide, 0.1 M hydrochloric acid and 0.1 M sodium hydroxide

Pharmacological Class: LHRH agonist

Zoladex[™] is supplied as a 10.8 mg solid depot formulation preloaded in a disposable syringe device mounted on a #14 gauge hypodermic needle. It should be administered subcutaneously every 12 weeks into the upper abdominal wall using sterile technique under the supervision of a physician. While a delay of a few days is permissible, every effort should be made to adhere to the q 12 week schedule.

8.8.2 ELIGARD[®] 22.5 mg

Active ingredient: Leuprolide acetate

Chemical name: 5-oxo-L-prolyl-L-histidyl-L-tryptophyl-L-seryl-L-tyrosyl-D-leucyl-L-leucyl-L-arginyl-N-ethyl-L-prolinamide acetate

Relative Molecular Weight: 1,209

Physical Appearance: Lyophilized, white to off-white powder

Solubility: Soluble in water and in acetic acid

Pharmacological Class: Synthetic non-peptide GnRH agonist

Eligard is provided as a powder and solvent for solution/suspension for injection (prolonged release), provided as 2 sterile, pre-filled, polypropylene syringes. One syringe contains the LA powder and the other syringe contains the Atrigel[®] Delivery System. When reconstituted,

ELIGARD[®] 22.5 mg injection is a white to off-white, opaque, viscous liquid. It should be administered once every 3 months.

8.9 KLH Protein

This clinical-grade KLH (Immucothel), used as a “heterologous helper antigen”, is being provided by Biosyn. It has previously been approved for use in our concurrent melanoma trial: UPCI 03-118/BB-IND 11,754, IRB# IRB0507089). KLH will be loaded only on α DC1s used in the first cycle of vaccination (first vaccine) and will be used as a one of the readouts of the ability of the vaccines to induce DTH responses (see secondary endpoints): the strategy used in our currently active melanoma protocol UPCI 03-118.

9 STATISTICAL CONSIDERATIONS

9.1 Study Design and Endpoints

This is a 2 group crossover trial in which subjects are randomly assigned to one of two treatment arms:

- 3 months of androgen ablation (AA) to be followed at PSA progression by 3 months of the combination of AA and alpha-type 1 dendritic cell vaccine (DCV)
- 3 months of the combination of AA and alpha-type 1 dendritic cell vaccine followed at PSA progression by 3 months of AA.

The primary objectives of this novel trial are to evaluate feasibility, safety, and a preliminary estimate of efficacy. Following either treatment arm the time to PSA progression, defined as the time between treatment and the first instance of PSA increase to 1.0 ng/mL, will be estimated from monthly PSA monitoring. The efficacy endpoint is the difference between time to PSA progression for the combination of AA + DCV compared to AA alone.

9.2 Number of Subjects

For the feasibility objective, the goal is to evaluate the production of bulk vaccine, storage of vaccine, and subsequent administration. If this is successful in the first 4 subjects, we will go on to accrue a total of 12 subjects, 6 per arm, for safety testing, with 6 subjects per arm being consistent with a standard Phase I design.

9.3 Characteristics of the Design

The difference in PSA progression between AA and AA + DCV will be calculated for each individual subject. We note that if the standard deviation of this difference is 1.5 months, a one tailed signed rank test at $\alpha = .05$ will have 98% power to detect a improvement of 1.8 months, equivalent to a hypothesized 30% improvement in time to PSA recovery (6 months vs 7.8 months).

9.4 Safety Evaluation

Serious adverse events are uncommon in cancer vaccine trials. For example, no treatment-related deaths or grade 4 toxicities have occurred among 652 subjects enrolled in Phase I studies by CTEP, NCI's Cancer Therapy Evaluation Program (Horstmann et al., 2005). Rather than a separate phase of the study to characterize vaccine safety, we will use continual Bayesian monitoring of SAEs (Berry, 2006) with a stopping rule that permits the investigator to suspend the trial for review by the Data and Safety and Monitoring Committee (DSMC). We have selected prior probabilities of SAEs to conform to our prior beliefs that the probability of a treatment-related SAE, caused by α DC1 vaccine is as low as 5%. The prior probability distribution was selected to permit at most a 10% chance that this prior probability could be double the expected prior probability. Assuming the prior probability follows a beta distribution, the stopping rule will be based on the updated posterior probability of an SAE, which also has a beta distribution. As each subject is observed for an SAE, the posterior probability of an SAE can be calculated. If at any time during the trial the probability is $\geq .50$ that the treatment-related SAE rate exceeds 5%, the study will be suspended pending review by the DSMC. In order to permit continuous monitoring of serious toxicities, a look-up table has been provided (below). This table is based upon cumulative observed SAEs at any point in the trial and can be used to signal when the therapy should be suspended and the trial results reviewed by the DSMC.

TABLE 4. Number of Observed Treatment-Related SAEs and Associated Posterior Probabilities Needed to Suspend the Study

Subjects	Total Observed SAE's	$\Pr(\pi \geq .05)^*$	$B(\text{SAE})^{**}$
1	1	.690	.05
2	1	.675	.098
3	1	.660	.143
4	1	.645	.186
5	1	.630	.226
6	1	.615	.264
7	1	.601	.302
8	1	.586	.337
9	1	.572	.370
10	1	.558	.401
11	1	.543	.431
12	1	.529	.460

π is the posterior probability of a treatment-related SAE. $\Pr(\pi \geq .05)$ is the chance that the posterior probability of a treatment-related SAE given the observed number of subjects treated and observed SAEs, exceeds .05.

** B is the binomial probability of observing at least the number of SAEs in column 2 if the underlying rate of SAE is 5%.

This table presents the minimum number of SAEs that dictate suspension of the trial in accordance with the stopping rule. According to this table a single SAE due to the α DC1-based vaccine among any of the 10 subjects will trigger suspension and review by the DSMC.

9.5 Data Analysis

Subjects will be required to have monthly PSA monitoring. This will enable linear interpolation between PSA samples to detect the time at which PSA progression occurs following each course of therapy. The efficacy endpoint is estimated by the difference between time to PSA progression for the AA+DCV arm and the AA arm. This difference will be tested for significance with a one tailed signed rank test. Other conventional estimates of clinical efficacy will also be calculated including PSA doubling time and PSA velocity. The PSA-DT will be calculated as follows:

The logarithm of a minimum of two PSA measurements will be plotted against the time of each PSA measurement. If 3 or more measurements are available a linear regression equation will be estimated. Two sequential PSA measurements (actual or estimated by linear regression) will be denoted as PSA1 and PSA2. Denote their times of blood samples as t1 and t2, respectively. Thus the PSA doubling time is: $\log(2)[t2 - t1] / [\log(\text{PSA}2) - \log(\text{PSA}1)]$.

Further analysis will involve testing the immunologic response of subjects receiving the α DC1-based vaccine. The principal measure of improved immunogenicity will be the comparison of pre to post α DC1-based vaccine T cell response to prostatic acid phosphatase (PAP) as measured by the IFN- γ Elispot assay. We expect that prostate cancer subjects undergoing androgen ablation in the absence of immune stimulation will have a negative or very low Elispot count for measuring reaction to PAP. Even with a nominal count of 5 spots in the group, a sample of 7 subjects with androgen ablation alone and 7 subjects treated with androgen ablation + α DC1-based vaccine will provide 90% power to detect a difference of double the Elispot count (average of 5 to 10 spots) using a one tailed alpha level Wilcoxon test if the Elispot counts have a Poisson distribution. Additional immunologic testing will be conducted by analyzing subject profiles before treatment and after each course of therapy. Immunologic endpoints include T cell reactivity by IFN γ or IL-5 Elispot, cytokine release assays for cytotoxicity and DTH tests (as measured by induration in mm). Changes over time will be tested with the Friedman Test or, if there are missing values, the Mack-Skillings procedure.

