5 STUDY DESIGN AND METHODS

This is a 2 group crossover trial in which subjects are randomly assigned to one of two treatment arms:

Cohort A: 3 months of androgen ablation (AA) to be followed at PSA progression by 3 months of the combination of AA and alpha-type 1 dendritic cell vaccine (DC1).

Cohort B: 3 months of the combination of AA and alpha-type 1 dendritic cell vaccine followed at PSA progression by 3 months of AA.

In this crossover trial each subject will serve as their own control. Following either therapy the time to PSA progression is defined as the time between treatment and the first instance of PSA increase to 1 ng/mL. The endpoint is the difference between the time to PSA progression for the combination of AA + DC1 compared to AA alone. A **total of 12 evaluable subjects** (6 subjects/arm) will be enrolled on the trial. Subjects who do not complete both courses (AA and AA+DCV) will be replaced. This schema will also help us better estimate the time to PSA recovery following 3 months of limited androgen ablation in our cohort of subjects.

All subjects in Cohort B will commence α DC1-based vaccination 2 weeks prior to treatment with the LHRH analogue. Each subject will receive 1 intradermal (*i.d.*) dose of the vaccine at weeks 1, 5, 9, and 13 for a total of 4 doses. The first dose will be considered the ‘priming’ dose and injections on weeks 5, 9, and 13 are ‘booster’ doses. Depending upon cells/volume the injections may utilize 1-2 syringes being administered on a single day. Additional courses of vaccination, if available after the 4 intended protocol doses, can be administered to any subject without evidence of disease progression, every 3 months (\pm 1 month) for up to 12 months. The schema for the vaccine can be found on page 6.

The LHRH analogue (Lupron 22.5 mg or Zoladex 10.8 mg) will be administered 2 weeks after the 1st dose of the DC vaccine.

We assume that 3 months of AA alone will be followed by PSA progression at a median of 6 months with 90% of PSA recovery times between 5 and 7 months. We suspect that a second course of AA will delay time to testosterone recovery by approximately 10% and that testosterone recovery and PSA failure will likely correlate very closely. Therefore we anticipate that a second course of AA will delay time to PSA relapse by approximately 10%. The purpose of randomizing to one of two treatment sequences is to permit an unbiased estimate of

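### The primary signed-rank test ignores treatment sequence although the plan expects a second-course delay: slightly conservative at 6:6, but its level depends on a balance that the plan does not expressly secure

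*Combined protocol and SAP*

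**What the plan says.** Section 5 assumes that AA alone is "followed by PSA progression at a median of 6 months with 90% of PSA recovery times between 5 and 7 months". It then anticipates that "a second course of AA will delay time to PSA relapse by approximately 10" per cent. On the purpose of the two sequences it says: "The purpose of randomizing to one of two treatment sequences is to permit an unbiased estimate of" the vaccine's contribution, whatever the variability of the second course.

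Section 9.2 sets the size: "we will go on to accrue a total of 12 subjects, 6 per arm". Section 5 likewise asks for 12 evaluable men, 6 per arm, and replaces those who do not complete both courses. It does not say in which sequence the replacement is made. Section 9.6 names an e-mail randomisation program and describes no blocking.

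Section 9.3 gives the power. It takes the AA+DCV minus AA difference for each man and states that, "if the standard deviation of this difference is 1.5 months", a one-tailed signed-rank test at 0.05 "will have 98% power to detect a improvement of 1.8 months". Section 9.5 repeats the test: "This difference will be tested for significance with a one tailed signed rank test". Neither section mentions sequence or period.

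**The concern.** The design has a feature for separating the vaccine effect from the course effect, and the analysis does not use it. A one-sample test on pooled differences treats all 12 men as having the same expected difference. Under the plan's own assumption they do not. A man in Cohort A receives the vaccine in his second course, so the delay adds to his difference. A man in Cohort B receives AA alone second, so the delay subtracts from it.

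If the cohorts contribute equal numbers, the two shifts cancel in the mean and remain as extra spread. If they do not, part of the course effect stays in the estimate, and it favours the vaccine whenever Cohort A has more evaluable men. At stake are some wasted significance level in the planned case, and a test whose error rate moves with the split in any other.

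**Working it through.** **Inputs.** n = 12, 6 per cohort (section 9.2). SD of the difference 1.5 months, effect 1.8 months (6 against 7.8), one-sided 0.05 (section 9.3). AA-alone median 6 months, second-course delay 10% (section 5). Assumed here: normal differences, and an additive delay of 0.10 × 6 = 0.6 month.

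**1. The plan's own figure.** The exact signed-rank test for n = 12 rejects when the positive-rank sum is at least 61, with an attained level of 4.6%. With no course effect, simulation gives power of 98.2%. The stated 98% is reproduced.

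**2. Expected differences with the delay.**
- Cohort A: (7.8 + 0.6) − 6 = 2.4 months; with no vaccine effect, +0.6.
- Cohort B: 7.8 − (6 + 0.6) = 1.2 months; with no vaccine effect, −0.6.

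At 6:6 the pooled mean is (2.4 + 1.2)/2 = 1.8, so it is unbiased. The pooled SD rises to √(1.5² + 0.6²) = 1.62.

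**3. Pooled signed-rank test by evaluable split.** The unequal splits are assumptions; the protocol does not predict them. Bias = 0.6 × (nA − nB)/12.

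| Split A:B | Bias (months) | Level | Power |
|---|---|---|---|
| 6:6 | 0 | 3.5% | 97.3% |
| 7:5 | +0.1 | 5.6% | 98.4% |
| 8:4 | +0.2 | 8.5% | 99.1% |
| 5:7 | −0.1 | 2.2% | 95.7% |
| 4:8 | −0.2 | 1.3% | 93.7% |

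The higher power at 7:5 and 8:4 comes from the upward bias and is not a real gain.

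**4. Sensitivity.**
- Multiplicative delay at 6:6 (7.8 × 1.1 − 6 = 2.58 in A, 1.2 in B): power 98.0%.
- If 1.5 is the total SD, so that the within-cohort SD is √(1.5² − 0.6²) = 1.37: at 6:6, level 3.4% and power 98.7%.
- If the SD is derived from the range of 5 to 7 months (1/1.645 = 0.61 per course; 0.61 × √2 = 0.86 for the difference, assuming independent courses): power about 100%. The level is 2.1% at 6:6, 4.8% at 7:5 and 10.3% at 8:4.
- Averaged over unrestricted 1:1 randomisation of 12 men (SD 1.5): level 4.6%, power 96.6%.

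**5. Using the sequence.** Take second-minus-first-course differences. With no vaccine effect both cohorts expect +0.6, so the course effect drops out of the comparison at any split. With the vaccine effect, A expects 2.4 and B expects −1.2. Half the gap is 3.6/2 = 1.8.

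For the t test with 10 df, SE = 1.5 × √[(1/nA + 1/nB)/4].
- 6:6: SE 0.433, non-centrality 1.8/0.433 = 4.16, power about 98.7%.
- 8:4: SE 0.459, non-centrality 3.92, power about 97.7%.

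Its level is 5.0% at every split examined. The exact rank-sum version has level 4.7% and power 97.8% at 6:6. Its power falls to about 96.5% at 7:5 and 94.6% at 8:4.

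**The case against.** A reader might infer that the 98% power and the 5% level fail under the plan's own assumptions. The documents do not support that. Those assumptions include 6 evaluable men per arm, and there the level is below 5% and power is within a point of 98%. If section 9.3 means 1.5 as the SD of all the differences, course spread included, there is no shortfall at all.

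A reader might also infer that the vaccine will be credited with the course effect. That requires more evaluable men in Cohort A, which nothing in the protocol predicts. Section 5 asks for 6 per arm in the sentence just before the replacement rule, so replacement within arm is a natural reading. Even with unrestricted randomisation the level averages 4.6%. At 8:4 the bias is 0.2 month against a target of 1.8. Section 9.1 calls efficacy a preliminary estimate, and at 6:6 the pooled mean equals the sequence-averaged mean.

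All of this stands, and it limits the point. What it leaves is that balance is a target and not a stated procedure. Section 4.4 expects 12 to 16 entrants, so replacements are foreseen. Evaluability requires both courses, and the vaccine-related exits in sections 6.3 and 6.6 fall at different stages in the two cohorts. An average level of 4.6% over possible splits does not help a trial that ends at 8:4.

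**Conclusion.** The point holds in a limited form. The primary test ignores a course effect that the plan itself expects. At the planned 6:6 split the cost is small: a level of about 3.5% where 4.6% is attainable, and power of about 97.3%. The stated 98% and 5% should not be called wrong.

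The weakness is dependence on balance that sections 5 and 9.6 neither expressly secure nor rule out. Over the assumed splits from 8:4 to 4:8, the level runs from about 8.5% to 1.3%, and power falls to about 94% when Cohort B is larger. These figures rest on normal differences, SD 1.5 within cohort and a 0.6-month additive delay. With the smaller SD implied by section 5, 7:5 stays just under 5% while 8:4 reaches about 10%. This is a cheap improvement, not a flaw that invalidates the planned analysis.

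**What to change.** In section 9.5, make the primary test a comparison of second-minus-first-course differences between Cohorts A and B, preferably the two-sample t test with pooled variance, one-sided at 0.05. Estimate the vaccine effect as the average of the two sequence-specific mean differences (AA+DCV minus AA), with a confidence interval. In section 9.3, keep the 98% power statement but attach it to this test and state n = 12, 6 per sequence. It would also help to state in sections 5 and 9.6 that randomisation is blocked and that replacements enter the same sequence. That supports balance, but only the adjusted test protects against imbalance that remains.

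The cost is wording: no additional men, visits or data. The t test relies on approximate normality with 12 men. The exact rank-sum test avoids this and performs nearly as well at 6:6, but loses power at unequal splits (about 96.5% at 7:5 and 94.6% at 8:4). Neither version deals with a vaccine effect that carries over into Cohort B's second course; the present test does not either.

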7 STUDY EVALUATIONS AND STUDY CALENDAR

7.1 Screening

Baseline evaluations are to be conducted within 14 days prior to the leukapheresis .. Scans and x-rays must be done within six weeks prior to the start of therapy.

- Complete physical examination (with ECOG performance status (PS), weight, height, and BSA)
- Radiologic imaging to evaluate the status of disease (all scans must be obtained within 30 days of starting therapy): Includes bone scan and CT scan of chest (or CXR), abdomen, and pelvis.
- Chemistry profile including: electrolytes, creatinine, blood urea nitrogen, glucose, SGOT, SGPT, total bilirubin, calcium, and albumin.
- Serum testosterone
- PSA levels in the blood (as a tumor marker). To be eligible, subjects must have at least two PSA levels checked at least 2 weeks apart, shown to be rising, and with the the last PSA being ≥ 2.0 ng/dL
- CBC, differential, platelet
- ANA Testing (if clinically indicated)
- Known history of HIV, HbsAg, and Anti-HCV. For subjects at high risk of HIV/viral hepatitis, HIV/viral hepatitis testing will be performed to confirm status.
- Following confirmation of eligibility, based on the above tests and procedures, the following, additional pre-treatment procedures will be performed:
 - Leukapheresis – for vaccine production and a portion will be obtained for *in vitro* assays (immune parameters of CD4⁺ and CD8⁺ T cell responses against tumor-associated and tumor-irrelevant control antigens).

- DTH placement within 48-72 hours before the day of first dendritic cell vaccine administration (baseline testing) to allow for it to be read on the day of and prior to the 1st vaccine injection.

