7.3 Post-Treatment

- Complete history and physical examination.
- For subjects with suspected disease progression on therapy, radiographic imaging as indicated.
- PSA at week 17, 21, and every 4 weeks thereafter. Confirmatory PSA should be performed 1 month post progression
- Testosterone at week 17, 25, and every 2 months thereafter
- CBC, differential, platelets at week 25 and every 3 months thereafter
- Chemistry profile (see Section 7.1) at week 25 and every 3 months thereafter
- Blood for in vitro assays (immune parameters of CD4+ and CD8+ T cell responses against tumor-associated and tumor-irrelevant control antigens) will be obtained 1 week and 6 weeks after completion of treatment. The assays will involve the evaluation of cytokine production, cytotoxicity, and changes in cell phenotype of T cell subsets.
- Leukapheresis - a second limited leukapheresis will be performed during week 19 to facilitate immune-monitoring.
- DTH testing (post-testing: 2 to 4 weeks after last vaccine, i.e., during week 15 through 17). The subjects will be asked to agree to the biopsies being taken from the sites of the DTH tests, following their readout.
- EPIMAX analysis may be used to define the magnitude and cytokine production profiles of CD4+ and CD8+ T cell responses to the overlapping peptide libraries and individual peptides covering the entire span of PAP and PSMA molecules
- Subjects with lack of disease progression at 12 months after the last treatment may be monitored for disease free survival, as well as for overall survival.

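### With one DTH test before and one after vaccination, the Friedman test in 9.5 is a sign test; the signed-rank test would usually be somewhat more efficient at no cost

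*Combined protocol and SAP*

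**What the plan says.** **The test.** Section 9.5 (Data Analysis) names DTH induration in mm within a list that also holds the ELISPOT and cytotoxicity assays: "cytokine release assays for cytotoxicity and DTH tests (as measured by induration in mm". It then states: "Changes over time will be tested with the Friedman Test or, if there are missing values, the Mack-Skillings procedure". DTH is not exempted. The same section introduces the group as "analyzing subject profiles before treatment and after each course of therapy".

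**The schedule.** Section 7.1 sets the first test: "DTH placement within 48-72 hours before the day of first dendritic cell vaccine administration (baseline testing". Section 7.3 sets the second: "DTH testing (post-testing: 2 to 4 weeks after last vaccine, i.e., during week 15 through 17". The calendar in 7.5 marks the skin test at baseline and in both the week 15 and the week 17 columns. The two later marks carry the same note c, which describes a single window.

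**The measure.** Section 8.5.2 defines a positive response as an "increase of 3 mm of induration post dendritic cell vaccine over pre-dendritic cell vaccine". It mentions no assessments other than pre and post: "Vehicle only will be used as a negative control in both pre- and post- dendritic cell vaccine evaluations".

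**The plan's own paired test.** For the within-subject primary endpoint, 9.5 says: "This difference will be tested for significance with a one tailed signed rank test".

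**The concern.** DTH in all subjects is a secondary objective (section 1.2), and the measurement is a length in millimetres. A test that reduces each man to rose or fell treats a 1 mm rise and a 10 mm rise alike. With 12 men that coarseness can cost power, and the plan already uses a paired test that retains the size of change. At stake is the efficiency of one secondary analysis. The validity of that analysis and the primary endpoint are not affected.

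**Working it through.** **1. The plan's own signed-rank figure.** Inputs from 9.3: difference 1.8 months, SD 1.5 months, one-tailed alpha 0.05. From 9.2: 12 subjects. The standardized effect is 1.8/1.5 = 1.2. The exact one-sided signed-rank test at n = 12 rejects at W+ ≥ 61 (level 0.0461). Simulated power with normal differences is 98.2%, which agrees with the stated 98%. No power is stated for DTH.

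**2. What Friedman becomes with two time points.** Let S be the number of men whose induration rose, with no ties. Then Q = (2S − n)²/n. For n = 12:

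| S | Q | chi-square p | exact two-sided sign p |
|---|---|---|---|
| 9 | (18 − 12)²/12 = 3.00 | 0.083 | 0.146 |
| 10 | (20 − 12)²/12 = 5.33 | 0.021 | 0.0386 |
| 11 | (22 − 12)²/12 = 8.33 | 0.004 | 0.006 |

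So at least 10 of 12 men must rise. The exact two-sided level is 2 × (66 + 12 + 1)/4096 = 0.0386.

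**3. An invented illustration.** Nine men rise by 4 to 10 mm and three fall by 1 to 2 mm. Friedman gives Q = 3.00, p = 0.083. For the signed-rank test the falls hold the three smallest ranks, so W− = 1 + 2 + 3 = 6. Of the 4096 sign patterns, 14 give W− ≤ 6, so p = 2 × 14/4096 = 0.007.

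**4. Power at n = 12, both tests two-sided at nominal 5%.** Exact levels are 3.9% (Friedman/sign) and 4.2% (signed-rank, W+ ≥ 65). Sign-test power is the binomial probability of 10 or more rises out of 12, with p the chance that a man rises. Under normal differences at 0.8 SD, p = Φ(0.8) = 0.788, and the three terms are 0.2740 + 0.1853 + 0.0574 = 0.517. Signed-rank power is simulated. Each cell shows Friedman, then signed-rank, then the gain in points.

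| Effect (SD) | Normal | Logistic | Laplace |
|---|---|---|---|
| 0.6 | 31.9%, 43.0%, 11.1 | 38.5%, 47.4%, 8.9 | 50.9%, 54.0%, 3.1 |
| 0.8 | 51.7%, 66.8%, 15.1 | 59.5%, 70.1%, 10.6 | 69.6%, 74.0%, 4.4 |
| 1.0 | 70.6%, 84.9%, 14.3 | 76.9%, 86.2%, 9.3 | 82.9%, 87.1%, 4.2 |
| 1.2 | 84.8%, 94.9%, 10.1 | 88.4%, 94.6%, 6.2 | 91.0%, 94.1%, 3.1 |

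**5. The case with no gain.** If every non-zero change is positive and zeros are dropped, both exact tests give p = 2 × (1/2)^m for m risers. With m = 6, p = 2/64 = 0.031 under each.

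**The case against.** **Two assessments is a reading, not an express statement.** The wording in 9.5 about each course, taken literally, implies three assessments, because every man has two courses. Friedman would then be a natural choice. The calendar also has two post-vaccine marks. Against this, note c and 7.3 describe one post-vaccine window, 8.5.2 defines response as post against pre, and no DTH visit is tied to the AA-alone course. Two time points is the better-supported reading. What stands is that 9.5 and the schedule do not match cleanly. If a third test was meant, the efficiency point falls away.

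**The Friedman sentence is shared wording.** It also covers assays on blood drawn four times (8.5), where it fits. That is so, and it is why the remedy is a carve-out for DTH rather than removal of the test.

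**The size depends on an undocumented distribution.** This stands. Induration cannot be negative. If baselines are near zero, which is an assumption but arguable for KLH, most changes would be zero or positive and the gain could vanish.

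**The millimetres are not lost from the plan.** Also correct: the 3 mm response definition uses them per subject, whichever test is chosen. The other half of the secondary objective, comparing the LNCaP response with the KLH response, is not addressed by a pre-to-post test per antigen. No decision rule or sample size rests on the DTH p-value.

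**Mack-Skillings is no remedy.** With two time points, a man missing one value supplies no pre/post comparison.

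**Conclusion.** The point holds as a minor efficiency matter. On the schedule as written, the planned DTH test is a two-sided sign test: valid, but blind to the size of change. The like-for-like gain from the signed-rank test at n = 12 runs from none to about 15 points. Where in that range it falls depends on assumed effect sizes and distributions.

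A reader might infer three stronger conclusions that the documents do not support:

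- **That Friedman is the wrong test.** It controls its level with two time points; it is only coarser.
- **That the loss is large.** That rests on the normal case alone, and the documents give no DTH SD to choose between the cases.
- **That power would rise from 52% to 80% at 0.8 SD, or from 71% to 93% at 1.0 SD.** Those higher figures are one-sided signed-rank power set against two-sided Friedman power. Section 9.5 specifies one-tailed testing for the primary endpoint and the ELISPOT power statement, not for DTH, so part of that gap is a change of level.

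**What to change.** In 9.5, state that pre-to-post change in DTH induration will be tested for each antigen with the Wilcoxon signed-rank test, and that Friedman or Mack-Skillings applies to endpoints with three or more time points. If a DTH assessment after the AA-alone course, or two separate post-vaccine tests, was intended, reconcile 7.1, 7.3, 7.5 and 8.5.2 with the wording in 9.5; Friedman can then stay. On the two-assessment reading the cost is one sentence, with no new data, visits or subjects. It should be settled before the DTH data are seen.
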